8. RANDOMIZATION

The study will use simple randomization in two groups: OrthoCor Active System and SOC. The randomization schema utilized will be consecutive enrolment at each site, alternatively in each group.

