8.0 STUDY DESIGN

8.1 Study Details

This is a prospective, multi-center, randomized, open label study that will enroll up to 100 subjects.

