8.3 Subject Population

The target population for this measurement consists of both males and females, presenting to the designated study sites with pain in superficial soft tissue, such as in the ankle, back, knee, wrist, elbow, shoulder, foot, or neck who are prescribed the use of the OrthoCor Active System or Standard of Care (SOC) intervention.

Eligible subjects must meet the inclusion and exclusion criteria described in Sections 8.4 and 8.5. Any questions from the investigative site regarding a potential subject's eligibility for enrollment must be discussed with the Sponsor (or designee) prior to consenting and enrolling the subject into the study for the investigational measurement.

It is estimated that up to 100 subjects may be enrolled into the study.

Patients will be enrolled consecutively at each participant site until up to 50 using the OrthoCor Active System and up to 50 using the Standard of Care (SOC) intervention have enrolled. The CRO will stratify the arms (OrthoCor Active System vs SOC) by selecting the arm alternatively. The patients will be enrolled consecutively at the participant site until enrollment is met.

As part of exploratory research extension, patients using the OrthoCor Active system will have the opportunity to continue on the trial for an additional 2 weeks. Participants assigned SOC have the opportunity to cross-over using the OrthoCor Active system for the additional 2 weeks. Participation in the exploratory extension is optional.

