9.2 Screening Process

Subjects will be prescreened for eligibility and if qualified will be approached with the study information and asked if they are willing to participate.

Informed consent will be obtained per section 14.2. All patients who sign a consent form are considered study subjects. A study participant is considered enrolled after they have signed an informed consent form and after the inclusion/exclusion criteria have been met.

After an IRB approved Informed Consent Form is obtained and study inclusion/exclusion criteria are met, the study assessment will begin immediately.

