15.2 Investigational Device Management

The OrthoCor Active System is FDA cleared for commercial use in the United States. The Sponsor shall maintain adequate records of the disposition of all investigational product for this trial. A copy of the Instructions for Use (IFU) will accompany each study device.

The OrthoCor Active System and pods will be distributed according to the Caerus process for subjects enrolled to use the device. The site will complete the subject enrollment form and email the completed form to [contact], the CRO, who will alternatively allocate the OrthoCor Active System or standard of care (SOC) to the enrolled subjects. Then, the Principal Investigator prescribes the enrolled participant who are allocated to the OrthoCor Active System group to receive the device using OrthoCor's Prescriber Prescription Form. This required documentation is then submitted to the Sponsor and the participant will receive a call from the Sponsor to confirm their address. The participant will receive their device in 3 to 5 days.

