4. STUDY DESIGN

This is a prospective, multi-center, randomized, open label study that will enroll up to 100 subjects. Subjects will consist of both males and females, presenting to the designated study sites with pain in superficial soft tissue, such as in the ankle, back, knee, wrist, elbow, shoulder, foot, or neck who are prescribed the use of the OrthoCor Active System or Standard of Care (SOC) intervention.

Patients will be enrolled consecutively at each participant site until up to 50 using the OrthoCor Active System and up to 50 using the Standard of Care (SOC) intervention have enrolled. The CRO will stratify the arms (OrthoCor Active System vs SOC) by selecting the arm alternatively. The patients will be enrolled consecutively at the participant site until enrollment is met.

As part of exploratory research extension, patients using the OrthoCor Active system will have the opportunity to continue the trial for an additional 2 weeks. Participants assigned SOC will have the opportunity to cross-over using the OrthoCor Active system for the additional 2 weeks. Participation in the exploratory extension is optional.

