9. BLINDING

The study is not blinded.

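### The trial is called randomized, but its operative allocation text describes alternation, and no random sequence or concealment is specified

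*SAP*

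**What the plan says.** The label is stated without qualification. Protocol 8.1: "This is a prospective, multi-center, randomized, open label study that will enroll up to 100 subjects". The Protocol 2.0 synopsis and SAP 4 use the same label.

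SAP 8 has two sentences. The first names a random method: "The study will use simple randomization in two groups: OrthoCor Active System and SOC". The second says how it is done: "The randomization schema utilized will be consecutive enrolment at each site, alternatively in each group".

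The other places that describe allocation are:

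- SAP 4: "The CRO will stratify the arms (OrthoCor Active System vs SOC) by selecting the arm alternatively". The same sentence stands in SAP 7 and Protocol 8.3.
- Protocol 15.2: the site emails the enrolment form to the CRO, "who will alternatively allocate the OrthoCor Active System or standard of care (SOC) to the enrolled subjects".

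Three further facts bear on the consequences. Arm sizes are capped (Protocol 8.3): "up to 50 using the OrthoCor Active System and up to 50 using the Standard of Care (SOC) intervention have enrolled". SAP 9 states: "The study is not blinded". Protocol 9.2 describes a selection step before consent: "Subjects will be prescreened for eligibility and if qualified will be approached with the study information".

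**The concern.** Randomization needs a chance mechanism that fixes the sequence and concealment of that sequence from those who recruit. The documents claim the first by name and describe neither. What they describe reads most naturally as strict alternation.

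The between-arm comparison of pain scores is the primary efficacy endpoint, and Protocol 18.4 foresees using the results in an FDA submission. Whether the arms were formed by chance is the basis for reading that comparison causally, so the label has to be right whatever the size of any bias.

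There is also a possible practical consequence. Treatment is open, the outcome is self-rated, and patients are prescreened before being approached. Someone who can foresee the next arm could let that influence whom to approach.

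**Working it through.** **1. Passages side by side**

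| Place | What it gives |
|---|---|
| Protocol 2.0, 8.1; SAP 4 | Label: randomized |
| SAP 8, sentence 1 | Names simple randomization |
| SAP 8, sentence 2 | Consecutive enrolment, arms taken *alternatively* |
| Protocol 8.3; SAP 4, 7 | CRO selects the arm *alternatively* |
| Protocol 15.2 | CRO allocates *alternatively* once it has the enrolment form |

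No place mentions a generated list, random blocks, a random start or concealment. The wording about stratifying the arms names no stratification factor; it describes the alternation itself. Even an assumed random start would leave only 2 possible sequences with one list, or 2^5 = 32 with five site lists.

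The 50/50 target does not follow from simple randomization either. For 100 subjects, P(exactly 50/50) = C(100,50)/2^100 = 0.080.

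**2. Predictability of the next arm**

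*Alternation within each site.* Past arms are visible, so each assignment after a site's first is known. With five sites and unknown starts, the expected share guessed is (100 − 5 × 0.5)/100 = 97.5%.

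*One sequence across sites, each site seeing only its own arms.* Let a site have enrolment share p. Its next subject comes G steps later, with G geometric(p), and receives the opposite arm when G is odd:

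P(G odd) = p / [1 − (1 − p)²] = 1/(2 − p)

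- p = 0.2 (five equal sites): 1/1.8 = 0.556
- p = 0.5 (two equal sites): 1/1.5 = 0.667
- p = 0.6 (one dominant site): 1/1.4 = 0.714

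**3. What steering could do (illustration only)**

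Everything here is assumed: no true effect, N = 100, five sites of 20, outcome SD 1, prognosis–outcome correlation 0.5, two-group t-test at two-sided 0.05. A recruiter passes over a candidate whose prognosis does not suit the expected arm with probability d.

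The share of suited candidates is then 1/(2 − d), against 1/2 without steering. The mean of the absolute value of a standard normal is √(2/π) = 0.798, and 95 of 100 assignments can be guessed at. With c the probability that the guess is right:

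shift = 2 × 0.5 × 0.798 × d/(2 − d) × 0.95 × (2c − 1)

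The standard error is √(2/50) = 0.20. For per-site alternation (c = 1) and d = 0.50, the shift is 0.798 × 0.333 × 0.95 = 0.253 SD. Dividing by 0.20 gives 1.26, and P(Z > 1.96 − 1.26) is about 24%.

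Simulation (10,000 trials per scenario) agrees:

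| Type I error at d = 0.10 / 0.25 / 0.50 | |
|---|---|
| Alternation within site | 5.6 / 8.1 / 24.6% |
| One alternating sequence, five equal sites | 5.0 / 5.3 / 5.0% |
| One random-order list, 50 per arm | 5.0 / 5.1 / 5.1% |

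The Monte Carlo standard error is 0.2–0.4 percentage points. The model covers neither the planned repeated-measures ANOVA nor the non-inferiority hypothesis of SAP 7.

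**The case against.** The first sentence of SAP 8 does name a random method. *Alternatively* can also loosely mean one or the other, and on that reading only the detail of sequence generation is missing. A reader might infer that the label fails under every possible reading; the documents do not support that, because they contradict themselves rather than being uniformly non-random. What stands against the loose reading is that arms are selected *alternatively* in a setting of consecutive enrolment, which makes strict alternation the natural sense. The loose reading also leaves both sequence and concealment unspecified.

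A reader might also infer that sites know every next arm, or that the comparison is already biased. Neither is supported. In SAP 8, the reference to each site may qualify only the consecutive enrolment, as similar wording does in Protocol 8.3 and SAP 4. Four sections have the CRO choose the arm, and none mentions site-level sequences. With one sequence over five equal sites the illustrative inflation is near nil; even with two equal sites and 50% steering it reaches only 7.1%. Consecutive enrolment, if followed, limits steering, and nothing in the documents shows that steering occurred.

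Release of the arm only after the enrolment form arrives is good practice, but it does not conceal a sequence that can be inferred from past assignments.

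**Conclusion.** The contradiction holds and should be resolved before any report calls this trial randomized. The conclusion rests on the text alone: a random label and a named random method on one side, and five sections describing *alternatively* chosen arms on the other, with no sequence or concealment anywhere. If arms are alternated as written, the design is quasi-randomised.

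The size of any bias is not established. Predictability runs from about 56% (one CRO sequence, five equal sites, each site seeing only its own arms) to certainty after a site's first subject (alternation within site), and the documents do not say which applies. Material type I inflation needs the within-site reading together with substantial steering; at 10% steering it is small even then. The need for correction does not depend on the simulation.

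**What to change.** Reconcile Protocol 2.0, 8.1, 8.3 and 15.2 with SAP 4, 7 and 8.

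**If enrolment is open.** Delete *alternatively* and the wording about stratifying the arms, and state:

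> Allocation is 1:1 from a single computer-generated list of 100 assignments, 50 per arm in random order, held by the CRO and concealed from sites. Each assignment is released only once the completed enrolment form has been received.

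If some subjects are already allocated, the list covers only the places remaining in each arm.

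This respects the cap of 50 per arm and is about 51% guessable with five equal sites. It replaces the term simple randomization in SAP 8 and does not balance arms within site. The point in Protocol 9.4 at which each group has 32 subjects would be reached after about 67 subjects on average, and at exactly 64 only about 16% of the time. The cost is a protocol and SAP amendment with IRB approval, and one list from a CRO that already allocates centrally.

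**For subjects already allocated by alternation.**

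- Replace randomized with *alternately allocated (quasi-randomised)*.
- State whether the sequence ran per site or across sites.
- Report baseline pain by arm and site.
- Add a sensitivity analysis adjusted for baseline pain and site, noting that it cannot remove unmeasured selection.

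The documents do not state whether enrolment is over. If it is, only this second part applies. The work is small, but the claim to randomization is lost.

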	
improvement in outcomes, but there is value in restorative therapies to help maintain functionality.
 
The Orthocor Active System delivers OrthoCor's patented Pulsed Electromagnetic Field (PEMF) therapy, a noninvasive, temporary relief for pain. The key to OrthoCor's therapy is the use of specialized PEMF technology. In particular, PEMF works at the source of injuries, and helps accelerate the body's natural anti-inflammatory and recovery responses. Inside every Active System is the OrthoCor, a microchip that delivers PEMF directly to the source of injuries. Furthermore, PEMF has been shown to stimulate reaction pathways that result in pain and inflammation reduction.

Study Assessment/ Evaluation:	Pain assessments will be conducted utilizing the Mankoski Pain Scale which will be compared to the pain assessments of subjects who were prescribed the Standard of Care (SOC) intervention.
Study Endpoints:	
Primary Safety Endpoint: The safety endpoint of this study will be the adverse events reported with the OrthoCor Active System pain after 2 weeks of use.
 
Primary Efficacy Endpoint: The efficacy endpoint of this study will be the comparison of the OrthoCor Active System pain assessment scores to the Standard of Care (SOC) intervention after 2 weeks of use.

Exploratory Assessment:	
Exploratory Assessment: The exploratory assessment of this study will be the performance of the OrthoCor Active System after an additional 2 weeks of use and is intended for research and publication only.

Number of Patients:	
Up to 100 subjects will be enrolled in order to achieve up to 50 using the OrthoCor Active System and up to 50 using the Standard of Care (SOC) intervention. The patients will be enrolled consecutively at the participant site until enrollment is met.
 
For the exploratory assessments, the 50 subjects who received SOC will have the opportunity to cross-over and use the OrthoCor Active system.

Number of Sites:	Five (5) sites are anticipated
Anticipated Study Duration:	3-5 months
Study Eligibility Criteria	
Inclusion Criteria:
 
Participants must meet ALL of the following:
 
 1. Individuals presenting with pain in superficial soft tissue, such as ankle, back, knee, wrist, elbow, shoulder, foot, or neck pain,

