8.2 Number of Clinical Sites

The trial will be conducted in up to five (5) participating sites in the USA.

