7. SAMPLE SIZE

The sample size estimates are calculated assuming a binomially distributed response of improvement or no improvement. Without any a priori estimates, the most conservative estimate (widest interval) is using a baseline for the standard of care (SOC) of 50% improvement. The null hypothesis for a non-inferiority study is that the experimental treatment is inferior to the standard of care. The alternative hypothesis is that the experimental treatment is non-inferior to the standard of care.

The sample size per group is based on the comparison of two proportions with baseline proportion of 50% for the experimental treatment assuming a 50% response for SOC and a non-inferiority margin of 10% assuming 90% power. The assumed confidence is 95% or a type 1 error rate of 5%.

The study will enroll 100 subjects, up to 50 using the OrthoCor Active System and up to 50 using the Standard of Care (SOC) intervention. The patients will be enrolled consecutively at the participant site until enrollment is met. The CRO will stratify the arms (OrthoCor Active System vs SOC) by selecting the arm alternatively.

For the exploratory assessments, the 50 subjects who received SOC will have the opportunity to cross-over and use the OrthoCor Active system.

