12. STATISTICAL ANALYSIS

The data consists of multiple repeated measures and will be checked for normalcy and sphericity, and primary analysis will consist of ANOVAs for repeated measures and with other secondary analysis as appropriate for secondary hypotheses. Nonparametric methods will be used if the data is not normally distributed.

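### The SAP describes alternation at each site but specifies no site term; if the alternation is per site, the primary test is slightly conservative (95% CI about 0% to 4.4% wider)

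*SAP*

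**What the plan says.** **Allocation.** SAP section 8 names the method in one sentence, "The study will use simple randomization in two groups: OrthoCor Active System and SOC", and describes it in the next: "The randomization schema utilized will be consecutive enrolment at each site, alternatively in each group". SAP section 7 adds: "The CRO will stratify the arms (OrthoCor Active System vs SOC) by selecting the arm alternatively". SAP section 4 and Protocol 8.3 say the same. None of these names site as a stratification factor. Protocol 15.2 has sites email enrolment forms to the CRO, "who will alternatively allocate the OrthoCor Active System or standard of care (SOC) to the enrolled subjects", and does not mention a separate list for each site.

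**Sites and blinding.** Protocol 8.2 allows "up to five (5) participating sites in the USA", and the synopsis says "Five (5) sites are anticipated". On masking, SAP section 9 says "The study is not blinded".

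**Analysis.** SAP section 12 says the "primary analysis will consist of ANOVAs for repeated measures", and SAP 11.1 also names this method. Neither lists factors, covariates or the contrast to be tested. Both provide for nonparametric methods if the data are not normal. The endpoint is the reduction in Mankoski score from baseline after two weeks (SAP 12.1). The documents give no site variance, no ICC and no confidence interval for the primary comparison.

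**The concern.** Alternation run separately at each site keeps the two arms within one subject of each other at every site. Site differences then largely cancel from the treatment contrast. An analysis without site still counts them as residual noise, so the standard error is larger than the design requires and the test rejects a true null hypothesis less often than its nominal 5%.

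Sites could plausibly differ in how pain changes. The documents do not define the content of SOC, so it may vary by site. Eligibility spans eight named body locations as well as over-exertion, strains, sprains and arthritis, so case mix may vary too. Complete-case analysis (Protocol 11.3, SAP 12.4) can also disturb within-site balance after allocation, and a site term would guard against that.

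What is at stake is a modest amount of precision, and an adjustment decision that would otherwise be made after the open-label data are visible.

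**Working it through.** The plan has no figure of its own to reproduce here. The sample-size statement in SAP section 7 concerns a binary response and does not involve site.

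**Inputs**
- From the documents: 100 subjects, 50 per arm (SAP 7); five sites (Protocol synopsis).
- Assumed: equal sites of 20, with 10 per arm at each.
- Assumed: site ICC of the analysed outcome, 0 to 0.10.

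**Step 1: per-site alternation.** Set the total variance to 1. With site in the model, the error variance is 1 − ICC on 100 − 6 = 94 degrees of freedom. With site omitted, five site effects of variance ICC add an expected 20 × 4 × ICC = 80 × ICC to the residual sum of squares, which has 98 degrees of freedom. So:

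- variance ratio (omitted/included) = [(1 − ICC) + ICC × 80/98] / (1 − ICC)
- CI-width ratio = √(variance ratio) × t98/t94, where t98/t94 = 1.9845/1.9855 = 0.9995

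At ICC 0.05: (0.95 + 0.0408)/0.95 = 1.043; √1.043 × 0.9995 = 1.021.

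At ICC 0.10: (0.90 + 0.0816)/0.90 = 1.091; √1.091 × 0.9995 = 1.044.

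Effective n is 100 divided by the variance ratio. It describes the information the reported interval reflects; with exact balance the point estimate itself does not change.

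**Step 2: simulation.** There were 6,000 runs per setting. The central-list setting placed subjects at five sites at random and alternated the arms over the whole list.

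| Assumed ICC | Variance ratio | Effective n | CI ratio, per site (formula) | CI ratio, per site (simulated) | Type I error, per site, site omitted | CI ratio, central list (simulated) | Type I error, central list, site omitted |
|---|---|---|---|---|---|---|---|
| 0 | 1.00 | 100 | 1.000 | 1.000 | 0.050 | 0.98 | 0.047 |
| 0.05 | 1.04 | 96 | 1.021 | 1.021 | 0.047 | 1.00 | 0.049 |
| 0.10 | 1.09 | 92 | 1.044 | 1.045 | 0.045 | 1.02 | 0.052 |

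The simulation error of a 5% rate is √(0.05 × 0.95/6000) = 0.003, so the conservatism at these ICCs is slight. It becomes clear at an ICC of 0.20: type I error 0.034 and an interval 9.7% wider under per-site alternation, against a width ratio of 1.07 under a central list.

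**Step 3: which site differences matter.** In a second simulation, subjects rated pain on 15 days (subject SD 1, daily SD 1) and a constant site shift in pain level was added with SD 0.3, 0.5 or 1.
- Change from baseline to day 14: standard error with the shift divided by that without was exactly 1.00.
- Within-subject error used for the group-by-time test: ratio exactly 1.00.
- Mean level over days, as in a group main effect: standard error ratio 1.03, 1.09 and 1.31.

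Only site differences in change matter for a change contrast. Site differences in level matter only if the group main effect is the test.

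**The case against.** The strongest objection is that within-site balance is one reading of unclear documents. SAP section 8 supports it, but also labels the method as simple randomization, and Protocol 15.2 fits a single CRO sequence just as well. A reader might infer that the interval is definitely wider than the design warrants. The documents do not support that: under a central list the arms are not balanced within site by design, and type I error stays near 0.05. This stands, and it is why the conclusion is conditional.

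Three other stronger readings also fail:
- **That the plan chose to exclude site.** It lists no model terms at all, so site is unspecified.
- **That all between-site pain differences stay in the error term.** The endpoint is change from baseline, and a constant site shift cancels. The SAP does not say which ANOVA contrast is primary, so a level effect cannot be ruled out, but it cannot be assumed either.
- **That the variance inflation is 1/(1 − ICC), or 1.05 and 1.11 at ICCs of 0.05 and 0.10.** With only five sites the ratios are 1.04 and 1.09.

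It is also fair to say that the direction is benign, since no excess of false positives arises. Any leakage of site differences into the contrast through drop-out is possible but has not been quantified. None of this removes the gain under the SAP's own wording.

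**Conclusion.** The point holds as a minor improvement. If alternation is per site, as SAP section 8 describes, omitting site makes the primary test slightly conservative. The 95% CI is about 0% to 4.4% wider (variance ratio 1.00 to 1.09, effective n about 92 to 100 of 100). If the CRO keeps one central list, the width ratio is about 0.98 to 1.02 and a site term is only an optional precision gain.

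These figures rest on five equal sites, 10 subjects per arm at each, and an ICC of 0 to 0.10 for the outcome actually analysed. The equal site sizes and the ICC are not in the documents.

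A reader might infer that a site term makes the allocation sound. It does not: strict alternation in an open-label trial lets the next assignment be predicted, and a model term cannot remove the selection bias that could follow. That is a separate and more serious problem.

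**What to change.** - State in SAP section 8 and Protocol 15.2 whether alternation runs per site or from one central list, and make the two agree.
- Name the primary contrast in SAP section 12, and include site as a fixed effect (up to five levels). If the test is group-by-time, site must also be crossed with time, because a site main effect alone does not remove site differences in change.
- Pre-state a rule for pooling small sites, such as a minimum number of analysed subjects per arm, fixed before outcomes are summarised by arm.
- If the nonparametric fallback is used, make it a site-stratified rank test, for example van Elteren.

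The cost is a few sentences in the SAP, up to 4 of about 98 degrees of freedom, and at most about 2% in CI width if sites do not differ (1/0.98 = 1.02, the central-list case at ICC 0). If the primary analysis has already been run, report the site-adjusted result as a clearly labelled supplementary analysis.
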